		1.1. Revision	
		Date(s)	
		add rows as needed	

Form CT UTHSA Clinical Trial Description

2. Background

Briefly discuss the important literature relevant to the trial and that provides background for the trial. Include the importance of the trial and any relevant treatment issues or controversies.

Type 2 Diabetes (T2D) is a significant problem in older adults and is known to increase the risk of future frailty. More than 25% of the U.S. population aged \geq 65 years has T2D; and, recent projections suggest that the number of cases of diagnosed T2D in those aged \geq 65 years will increase by 4.5-fold (compared to 3-fold in the total population) between 2005 and 2050. Although the burden of T2D is often described in terms of its impact on working-aged adults, the disease also affects longevity, disability, and common geriatric syndromes such as frailty, which ultimately leads inability to maintain independence. The combination of the T2D epidemic and increasing population of older adults call for innovative healthcare strategies and communication technology such as mobile health (mHealth) that can play a significant role in modifying the lifestyle behaviors of older adults in order to improve frailty characteristics and manage T2D. It has been supported that mHealth can facilitate behavior promotion (diet, physical activity), improve self-management, self-efficacy, and medication adherence in older adults. Research indicates that older adults have positive attitudes toward the use of mHealth interventions and applications and confident in their ability to self-manage their T2D suggesting that the benefits of technology outweigh the costs of adapting its use in this population. To the best of our knowledge, no study has reported on the impact of behavioral lifestyle interventions for overweight/obese older adults with T2D on improvements of frailty characteristics. For this pilot study, we will conduct a randomized controlled trial to determine the feasibility and compare the preliminary efficacy of a behavioral lifestyle intervention and its impact on frailty-related measures in overweight/obese community-dwelling older adults with T2D. We will be using mHealth tools to enhance self-monitoring of multiple behaviors (diet and physical activity) and to manage T2D. Our overall goal is to test the hypothesis that the implementation of behavioral lifestyle interventions to promote physical activity and dietary modifications will help older adults with T2D to improve frailty characteristics and manage the disease, which may eventually lead to healthy aging. Such intervention would include the use of self-monitoring of diet and physical activity.

3. Objectives and Endpoints All data points collected in the study should support an objective or have a regulatory *purpose.*

Complete the table – add rows as needed.

3.1. Objective(s) Clearly and concisely define the primary and secondary outcomes.	3.2. Endpoint Clearly define the endpoints. (endpoints are the basis for concluding that the objective has been met).	3.3. Justification for Endpoint Briefly explain why the endpoint(s) were chosen.
Determine the feasibility of the	Results from this study will	Behavioral lifestyle interventions using a
lifestyle intervention using a	provide the first information	smartphone for self-monitoring to
smartphone for self-monitoring of	regarding the efficacy of a	improve frailty measurements, body
diet and physical activity for the	behavioral lifestyle intervention	weight, and glycemic control in
improvement of frailty measurements	using a smartphone in the	overweight/obese older adults with T2D.

19-019H, [name], Form CT, 10-20-20, AMD

2

(primary outcome) and on weight management and glycemic control (secondary outcomes) in	improvement of frailty measurements in community- dwelling older adults with T2D.	
overweight/obese older adults with T2D.		

4. Rationale

Briefly state the reason for conducting the clinical trial.

Despite the significant prevalence of T2D among older adults and/or those with multiple comorbidities, these populations have been excluded from randomized controlled trials of treatments for T2D and its associated conditions. Based on the prevalence of T2D, its related complications, implementation of cost-effective treatment and up to date (or less burdensome) self-monitoring strategies for overweight/obese older adults with T2D, this study is needed.

5. Study Design: Randomized controlled trial																		
5.1. Number of					Group name(s)			mHealth+ group Intervention group										
Gro	oups/Arms								sup name(s) initiation group intervention group									
5.2.	Overall Des	sign																
Sele	ct all applic	able																
	□ Randomization								(Cluster I	Rando	omize	d					
	□ Group-Sequential						A	Adaptive	e Desi	gn								
	Parallel Design						P	Placebo-Controlled										
□ Superiority						F	Equivalence 🛛 Non-inferiority					y						
	Device		Pil	lot					P	Pivotal 🗆 Post-Approval								
Drug/Biologic \Box $Phase_1$ \Box Phase 1/2			e 1/2	: [Phase	2		Phase 2/3		P	hase 3		Phase 4				
$\Box \textbf{Dose escalation} \begin{array}{c} If yes, details \\ \rightarrow \end{array}$											-							
	$\Box \textbf{Dose ranging} \begin{array}{c} If yes, details \\ \rightarrow \end{array}$																	
	$\Box \textbf{Sub-studies} \begin{array}{c} If yes, details \\ \rightarrow \end{array}$																	
	5.3. Other Design Details : This will be a 6-month randomized controlled trial. The study will start after the approval from UT Health San Antonio IRB department. All study visits will be performed in the UT Health School of Nursing.																	

6. Study Population:		
6.1. Study Population(s)	6.2. Identify the criteria for inclusion	6.3. Identify the criteria for exclusion
Label/Name	The criteria that every potential participant must satisfy, to qualify for study entry.	The characteristics that make an individual ineligible for study participation.
To add more populations – select a row, copy & paste	All individuals in this study population must meet all of the inclusion criteria in order to be eligible to participate in the study	All individuals in this study population meeting any of the exclusion criteria at baseline will be excluded from study participation.

3

٧

Overweight/obese community-		Jnsafe to walk using EASY criteria or				
dwelling older adults with T2D	5	clinical judgement of the PI.				
	Men and women of all ethnic groups H	History of severe psychiatric disorders				
	Self-reported of provider-diagnosed with o	or cognitive impairment which interferes with active participation in				
	T2D for at-least 6 months.					
	Received basic diabetes self-	the study				
	management education R	Residence of long-term care facility				
		History of substance abuse in the past				
		/ear				
	the next 6 months.	Unwilling to be randomized in a				
	Overweight/obese (BMI ≥25 kg/m2 m	mHealth+ individual intervention group				
	Able to read and write in English					
	Own a smartphone					
	At PI discretion, participant is					
	willing/able to comply with the					
	protocol requirements					
6.4.	⊠ No □ Yes If yes, descr	ribe criteria below ↓				
Will screen failures be allowed						
to re-screen at a later date?						

7. Study Intervention(s) being tested or evaluated

This can include prevention, diagnostic or therapeutic interventions (e.g., drug or device) or educational, health services or basic science interventions (e.g., educational program, health care delivery model, or examining basic physiology)

Behavioral lifestyle intervention: Participants (N=40) will be randomized to the mHealth+ group Intervention group (Group A; n=20) and mHealth+ individual intervention group (Group B; n=20) group using a block randomization table. (1) The mHealth+ group Intervention group (Group A) will receive a modified Look AHEAD behavior lifestyle intervention with smartphone-based self-monitoring of diet and physical activity. This comprises ten group sessions for lifestyle intervention in 6-months. The group will receive three weekly classes in the first month and then bi-weekly classes for month 2-3, and three monthly session in month four, five, and six. The frequency and layout of these classes will allow participants to master new skills gradually, then eventually wean off, and adopt the modified lifestyle as the part of their daily lives. (2) The mHealth+ individual intervention group (Group B) will receive an abbreviated behavior lifestyle intervention with smartphone-based self-monitoring of diet and physical activity in one face-to-face individual session at the beginning of the study. In addition, participants will receive self-study materials, from Look Ahead modules, and a monthly follow-up phone calls for the duration of the study (6-months). The goal for these follow up phone calls are to assess understanding of the modules, to promote continued engagement with the study material, and to provide clarification on materials as needed. Participants in the mHealth+ group Intervention group (Group A) and mHealth+ individual intervention group (Group B will receive instruction on how to download an app to help them record their diet and physical activity at the beginning of the study. (see updates to study protocol dated below)

Fitbit offers a simple, easy-to-use tool for tracking food and physical activity. It helps set daily calorie budget, and set and work towards goals for nutrient intake, weight loss, exercise, and more. https://www.fitbit.com/inspire

04.12.20: Due to COVID-19 and social distancing order, we are adding hemoglobin Hba1c home test for our eight participants who are finishing the study on April 20, 2020. We have called all 8 participants and informed them about Hba1c home testing kit that will be delivered to their house after the final and tenth virtual session on April 20, 2020. We have confirmed their home address over the phone to mail the kit. Participants have been informed that the PI will explain and run the test individually with all 8 participants. Our next study group will finish the study in 2nd week of June, 2020. We will continue to follow our study participants and provide monthly behavioral educational sessions

4

in the group intervention, virtually, until the social distancing order will be lifted. Our study is not enrolling any new participants at this time.

On April 20, 2020, eight participants will finish the study and we will collect focus group questions virtually. We will also collect their individual questionnaire virtually to collect end of study assessments. Once the social distancing order will lift, we will collect face to face blood test and frailty assessments.

10.20.20: we finished our participants (N=20) in the group intervention and due to COVID-19 restrictions we were not able to enroll our participants for the control group (Group B). We talked with IRB staff and study team and decided to stop enrolling participating for the control group (group B) as the risk was higher based on the inclusion criteria for our study participants than the benefits for the control participants. Modification due to Pandemic, forgoing control arm, and worked with the interventional participants still worked with the study data to meet study aim-the deviation related to COVID-19 did not impact subject rights, safety, welfare, or the overall integrity of the science of the study.

8. Protocol-Directed procedures, items, services or tests

List all procedures directed by the study plan - including items or services provided as part of routine or conventional care and those needed to diagnosis or treat research related complications.

Important Note – The protocol directed procedures listed must match those in the Schedule of Activities (attachment) 8.1. Drugs (trade and generic, dosage, route of administration)

N/A

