10.2. Study Intervention Compliance

Define how adherence to the protocol (e.g., administration of study intervention, use of device,) will be assessed, and verified (if applicable, e.g., plasma assays, electronic monitoring devices, daily diaries).

The project is limited because we are enrolling only older adults from the community with T2D who carry a smartphone. In addition, given the significant commitment necessary to participate in the group sessions for the intervention group an attrition is an inherent potential issue. We will take several steps to minimize attrition including providing reimbursement and collecting multiple contact information (cell phone, home phone, email addresses) from the participants in order to remind them of the scheduled group sessions. We will also provide periodic updates to providers to remind them of the study and the importance of their support. The information gained from the pilot project will inform future interventions using mHealth tools toward community-dwelling older adults with T2D.

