12.1. Statistical Hypotheses

State the formal and testable null and alternative hypotheses for primary and key secondary endpoints, specifying the type of comparison (e.g., superiority, equivalence or non-inferiority, dose response) and time period for which each endpoint will be analyzed.

Behavioral lifestyle interventions using a smartphone for self-monitoring to improve frailty measurements, body weight, and glycemic control in overweight/obese older adults with T2D.

8

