12.4. Statistical Analyses

Include analysis of primary efficacy endpoints, secondary endpoints, safety analyses, and any planned interim analyses

The impact of the intervention on frailty status (non-frail, pre-frail, frail) and frailty score (0, 1, 2, 3, 4, or 5) over the 6month period (from baseline to follow-up) will be assessed by proportional odds cumulative logit (POCL) model to assess the log-odds of frailty as an indicator of being exposed to the intervention. The initial POCL model will adjust only for the baseline value of frailty status. A subsequent model will adjust for baseline age, sex, ethnic group, BMI, and Hba1c, to determine potential covariate interactions with the intervention. Continuous secondary outcomes including fasting glucose, Hba1c, and BMI will be assessed using linear regression with intervention, baseline frailty, sex, and ethnic group as categorical predictor variables and baseline age, BMI, and Hba1c as continuous predictor variables. The categorical outcomes SPPB and PROMIS scores will also be evaluated using the POCL model. Because the POCL model is complex and this is a pilot study, it is not practical or feasible to do a power analysis for the given experimental design but based on the work of Drs. [name] and [name], we believe at least 20 participants in the group (mHealth+ group Intervention group) are needed. The effect of the intervention on the change in frailty category and/or frailty scores will be used to calculate power and sample size estimation for a future, larger study.

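### Feasibility is a stated aim but has no endpoint or analysis, and with Group B never enrolled the plan yields neither a feasibility rate nor a controlled efficacy result

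*Combined protocol and SAP*

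**What the plan says.** - **Aim (Section 2).** The pilot is "to determine the feasibility and compare the preliminary efficacy of a behavioral lifestyle intervention".
- **Objective (3.1).** The cell opens with "Determine the feasibility of the" intervention. After naming frailty measurements it continues "primary outcome) and on weight management and glycemic control (secondary outcomes) in" the target population. Feasibility therefore leads the sentence, and frailty carries the primary-outcome label.
- **Endpoint (3.2).** The single entry promises first information "regarding the efficacy of a" smartphone-based intervention on frailty. The form's own instruction for this column is that endpoints are what one uses to conclude that the objective was met.
- **Hypothesis (12.1).** "Behavioral lifestyle interventions using a smartphone for self-monitoring to improve frailty measurements, body weight, and glycemic control". Feasibility does not appear.
- **Analyses (12.3 and 12.4).** Frailty status and frailty score "will be assessed by proportional odds cumulative logit (POCL) model to assess the log-odds of frailty as an indicator" of exposure to the intervention. Fasting glucose, HbA1c and BMI go to linear regression; SPPB and PROMIS go to the same ordinal model.
- **Adherence (10.2).** The form asks how adherence will be assessed and verified. The answer is "We will take several steps to minimize attrition including providing reimbursement", together with collecting contact details for reminders. No measure is given.
- **Focus group (8.6).** An audio-recorded end-of-study discussion covers which strategies helped, which did not, and plans for continuing. No analysis is described.
- **Amendment of 10.20.20 (Sections 7 and 10.1).** Group A finished with N=20, Group B was not enrolled, and the study aim is said to be met from Group A alone.

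**The concern.** An objective needs a measure by which to judge it. Feasibility has none in the sections where one belongs: 3.2, 10.2, 12.3 and 12.4.

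The loss of Group B makes the gap matter more. With two arms, the plan would at least have produced the between-group comparison that it describes. With one arm that comparison is gone, and feasibility is one of the few stated questions that 20 people in a single arm can still address. Section 10.1 says that Group A supplied enough information for the pilot. With no feasibility measure or criterion on file, a reader cannot check that statement.

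The next study is affected too. Section 12.2 intends this pilot to inform the size of a larger trial, and sizing a trial needs a retention estimate as well as an effect estimate.

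**Working it through.** **The plan's own figure.** Section 12.2 asks for at least 20 participants in the group arm, on the strength of earlier work. It declines a power analysis and gives no alpha, power, effect size, standard deviation, rate or dropout. The 20 cannot be reproduced, and nothing below depends on how it was chosen.

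**Step 1: set the aims against the endpoints and analyses.**

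| Aim | Endpoint in 3.2 | Analysis in 12.3/12.4 |
|---|---|---|
| Feasibility | none | none |
| Frailty (labelled primary) | efficacy on frailty | ordinal model, status and score |
| Weight, glycemic control (secondary) | none listed separately | linear regression: fasting glucose, HbA1c, BMI |
| SPPB, PROMIS | none listed | ordinal model |

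The number of feasibility analyses is 0. Sections 11.1 and 11.2 say only that participants may leave at any time, so they supply no retention measure either.

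**Step 2: what the 12.4 models can estimate with one arm.** Let *x* be the intervention indicator. The ordinal model has the form logit P(Y ≤ k) = α_k − βx − (baseline terms). With Group A alone, x = 1 for everyone, so only the differences α_k − β are identified. Any value of β fits equally well once the cut-points are shifted to match. In the linear regressions the intervention term is likewise a constant, inseparable from the intercept. No intervention effect can be estimated from either.

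**Step 3: what a feasibility proportion would look like.** The documents give no feasibility rate, so the counts below are assumptions. For x successes out of n, the exact (Clopper-Pearson) 95% limits are

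- lower = Beta⁻¹(0.025; x, n − x + 1)
- upper = Beta⁻¹(0.975; x + 1, n − x), or 1 when x = n.

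With n = 20:

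| Count | Proportion | Exact 95% CI |
|---|---|---|
| 12/20 | 60% | 36.1% to 80.9% |
| 16/20 | 80% | 56.3% to 94.3% |
| 18/20 | 90% | 68.3% to 98.8% |
| 20/20 | 100% | 83.2% to 100% |

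The 12/20 row has a concrete reading. Section 7 says that face-to-face frailty assessment was deferred for the eight participants finishing on April 20, 2020. If none of the eight were later assessed and everyone else was, completion would be 20 − 8 = 12 of 20. The documents do not say whether this happened. It shows only that completion of the primary measure was in real doubt and that no planned analysis would report it.

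**Step 4: which data are documented.** Baseline and end-of-study frailty assessments are specified in 8.6, so completion of both can be counted. The session plan in Section 7 gives 3 weekly + 4 bi-weekly + 3 monthly = 10 sessions, but no section describes an attendance record. Section 7 says that participants are shown how to download an app for recording diet and activity. It does not say that the study team retrieves the logs.

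**The case against.** **Frailty, not feasibility, is the labelled primary outcome.** This stands. The endpoint in 3.2 agrees with the label in 3.1, Section 2 states an overall goal of testing an effect on frailty, and 12.2 uses the frailty effect to plan a larger study. A reader might infer that 3.2 holds the wrong endpoint and that it should be replaced. The documents do not support that: replacement would leave the designated primary outcome without an endpoint. The defect is an omission, and an addition cures it.

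**The focus group addresses acceptability.** This stands in part. A reader might infer that the plan collects nothing on feasibility, which would be wrong, since 8.6 asks what worked and what did not. That material is qualitative, is not tied to the feasibility aim, has no analysis plan, and cannot yield a retention or adherence rate.

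**Attendance and app data may not exist.** This stands. The Schedule of Activities is an attachment that is not in the text reviewed, so it cannot settle the matter. Only completion of the frailty assessments can be relied on.

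**It is too late to prespecify a threshold.** This stands. The current text reports that Group A had finished, and Section 10.1 states that the investigator was not blinded.

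**COVID-19 distorts any rate.** This also stands. Up to three sessions moved to WebEx and some assessments were deferred, so the rates partly measure disruption. That is a reason to report them with a caveat.

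**Conclusion.** The point holds. Feasibility is a declared aim with no endpoint, no adherence measure and no analysis in the sections that should carry them. With Group B never enrolled, the 12.4 models cannot estimate an intervention effect. Followed exactly, the plan produces no quantitative feasibility result and no controlled efficacy result.

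The remedy is modest in precision. At an assumed 80% completion the interval runs from 56% to 94%, a width of 38 percentage points (94.3 − 56.3). That is informative about gross failure, but too wide to confirm that a threshold near 80% is met.

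The conclusion rests on two conditions. The missing attachment must not define a feasibility analysis; the objective, compliance and statistical sections, where one would be expected, are present and contain none. The denominator must also be settled: N=20 in the amendment could mean 20 who started or 20 who finished. If it means finishers, a proportion on 20 is close to 100% by construction and the number who started is unknown. Section 12.3 does not help, because it repeats the model description and names no analysis set.

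A reader might go further and expect a before-after frailty change to be published as the efficacy result. The documents say nothing about reporting, so that would be a guess.

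**What to change.** 1. **Add to 3.2 and 12.4** a feasibility endpoint: the proportion of all participants who started Group A with both baseline and end-of-study frailty assessments, with an exact 95% CI. Leave frailty as the labelled primary outcome.
2. **State the denominator**: whether N=20 means enrolled or completed, and how many started.
3. **In 10.2, define adherence from whatever records exist**: session attendance, split by in-person and WebEx, and app self-monitoring if the logs can be retrieved. If the records do not exist, say so.
4. **Report the focus-group findings under the feasibility objective**, with a short description of how they will be summarised.
5. **Note that COVID-19 disruption affects these rates**, and label any progression threshold as set after data collection.
6. **Present frailty, weight and HbA1c results** as uncontrolled, descriptive before-after changes.

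The cost is wording in three sections and a little tabulation. The intervals will be wide and the efficacy claim becomes weaker. Attendance and app summaries may cost more, or prove impossible, depending on what was kept.

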After discussing with IRB person and mentors, we decided to not to enroll participants for the Group B due to highrisk for COVID-19. We were able to receive enough information from the Group A intervention participants and to finish enrolling participants for the pilot study. Modification due to Pandemic, forgoing control arm, and worked with the interventional participants still worked with the study data to meet study aim-the deviation related to COVID-19 did not impact subject rights, safety, welfare, or the overall integrity of the science of the study.

7

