12.2. Sample Size Determination

Include number of participants to recruit, screen, and enroll to have adequate power to test the key hypotheses for the study. Provide all information needed to validate your calculations and judge the feasibility of enrolling and following the necessary number of participants.

Because the POCL model is complex and this is a pilot study, it is not practical or feasible to do a power analysis for the given experimental design but based on the work of Drs. [name] and [name], we believe at least 20 participants in the group (mHealth+ group Intervention group) are needed. The effect of the intervention on the change in frailty category and/or frailty scores will be used to calculate power and sample size estimation for a future, larger study.

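### The 3.2 endpoint is satisfied by any completed dataset, and the later trial is to be sized from an imprecise, uncontrolled pilot effect

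*Combined protocol and SAP*

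**What the plan says.** The objective in 3.1 opens with "Determine the feasibility of the" lifestyle intervention and names improvement in frailty measurements as the primary outcome. The form's own instruction for 3.2 is that "endpoints are the basis for concluding that the objective has been met". The entry made there is that results will "provide the first information" on efficacy for frailty. It gives no variable, time point, summary measure or threshold.

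Section 12.1, where the form asks for null and alternative hypotheses, holds a topic phrase. Sections 12.3 and 12.4 name a proportional odds cumulative logit (POCL) model with an intervention term. They give no significance level, and no estimate or interval is tied to a conclusion.

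The 10.20.20 entry in section 7 records that "we finished our participants (N=20) in the group intervention", that Group B would not be enrolled, and that the team "still worked with the study data to meet study aim". Section 10.1 adds: "We were able to receive enough information from the Group A intervention participants and to finish enrolling participants for the pilot study". Neither entry cites a frailty result.

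On the next step, section 12.2, repeated in 12.4, states: "The effect of the intervention on the change in frailty category and/or frailty scores will be used to calculate power and sample size" for a later study.

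**The concern.** There are two linked problems.

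First, the form makes the endpoint the test of whether the objective is met, and the entry made there cannot fail. Improvement, no change and worsening in frailty all satisfy it equally. A reader of the final report would have no pre-stated basis for telling a promising pilot from an uninformative one.

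Second, the plan does commit the pilot's frailty effect to one use, sizing a larger trial. A 20-person estimate is too imprecise for that. Without Group B it is also no longer an intervention effect: it is change over 6 months in one group, part of it under COVID-19 restrictions. An overestimate leads directly to a later trial that is too small.

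**Working it through.** **1. Does any section supply the missing rule?**

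| Section | What it supplies | Links a frailty result to a conclusion? |
|---|---|---|
| 2 Background | Directional hypothesis of improvement | No size or test given |
| 3.2 | Existence of results | No frailty value enters |
| 8.6 | Five-item frailty definition, baseline and end of study | Measure only |
| 12.1 | Topic phrase | No null or alternative |
| 12.2 | Effect used for later sizing | No criterion |
| 12.3, 12.4 | POCL model | No estimate or interval tied to a conclusion |

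Read as a rule on the number of the 20 who improve, 3.2 requires at least 0 of 20. That is met with probability 1 at every true improvement rate. For contrast, an illustrative rule of at least 6 of 20 is met with probability 0.011 at a true rate of 0.10 and 0.874 at 0.40.

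**2. The plan's own figure.** At least 20 in Group A, with no inputs, so it cannot be reproduced. At an assumed two-sided 5% level and 80% power, 20 per arm would match a standardised difference of √(2/20) × (1.960 + 0.842) = 0.886.

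**3. What Group A alone can estimate.** With columns for intercept, intervention and two baseline-status indicators, the design has rank 4 of 4 with both groups and 3 of 4 with Group A only. The intervention column is then constant, so its coefficient cannot be estimated. What remains is within-person change.

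**4. Precision of that change.** Half-width = t(0.975, 19)/√20 = 2.093/4.472 = 0.468 SD of change. Section 7 deferred face-to-face frailty assessment for eight participants and reports no later collection. If those were missing (an assumption), n = 12 and the half-width is 2.201/3.464 = 0.635 SD.

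**5. Sizing from the point estimate.** Assumptions, none from the documents:
- baseline scores 0 to 5 at 35/30/20/10/4/1%, from a latent normal variable;
- baseline to follow-up latent correlation 0.6 or 0.8;
- latent improvement 0 or 0.4, the latter giving a true score change of 0.37 SD (correlation 0.6) or 0.48 SD (correlation 0.8);
- the same standardised effect holding as the between-arm difference in the later trial.

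For each of 40,000 simulated pilots at n = 20, the standardised estimate d gives N per arm = 2(1.960 + 0.842)²/d² = 15.70/d². True power at that N is Φ(δ√(N/2) − 1.960), where δ is the true standardised change.

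| True change | Mean score favourable | 95% CI wholly on improvement side | Later trial under 80% power, among favourable pilots |
|---|---|---|---|
| 0 | 45–46% | 2.5% | not applicable |
| 0.37 SD | 94% | 35% | 55% |
| 0.48 SD | 98% | 54% | 52% |

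With no true change, favourable pilots give a median N of about 535 per arm and a 10th percentile of about 99. If score or category may count, as the and/or wording in 12.2 allows, 53% look favourable.

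The figure of about one half is not peculiar to the assumed distribution. The later trial is too small whenever d exceeds δ, and a roughly unbiased estimate does that about half the time.

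**The case against.** The strongest reply is that 3.2 is one poorly completed cell and the rest of the document does the work. Frailty is named as the primary outcome, defined in 8.6 and modelled in 12.4, and a null or adverse result could be produced and reported. That is correct, and it limits the point. A reader might infer that a favourable efficacy conclusion is fixed in advance, or that the pilot cannot answer its question at all. The documents support neither. What stands is narrower: no text says what a given frailty result would mean for the objective.

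A reader might also infer from the 10.20.20 entries that the aim was declared met because Group A finished. The entries say the data were used toward the aim, and the sentence about enough information explains why enrolment stopped. They state purpose and sufficiency, without a criterion, but they do not declare success.

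On sizing, section 12.2 does not commit anyone to running a larger trial, and a weak estimate gives a discouragingly large N. That is a partial safeguard. It does not help when chance makes the estimate too large, which is the case that produces an underpowered trial. It is also fair that the simulation uses a single assumed baseline distribution.

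Finally, formal go/no-go rules in a 20-person pilot are partly a matter of preference. Because change here is uncontrolled and overlaps COVID-19 restrictions, a rule that worsening rules out a larger study would not be justified.

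**Conclusion.** The point holds in two parts. The first needs no assumptions: the 3.2 endpoint is not measurable, any completed dataset meets it, and nothing in 12.1 or 12.4 makes the formal conclusion on the objective depend on frailty.

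The second is that sizing a later trial from this pilot's effect is unsound. The half-width of 0.47 SD of change follows from n = 20 alone and assumes all 20 have end-of-study frailty data. Under the assumed score distribution and correlations, 45–46% of no-change pilots would look favourable and yield a finite N, and at a true change of 0.37–0.48 SD, 52–55% of trials sized from favourable pilots would have under 80% power. Carrying an uncontrolled change over as a between-arm effect is itself an optimistic assumption.

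No figure in the plan is shown to be wrong.

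**What to change.** 1. **Section 3.2.** State the endpoint as within-person change in frailty score (0 to 5), with frailty status alongside, from baseline to 6 months. Report it with its 95% CI, label it uncontrolled, and give the number of the 20 with end-of-study frailty data. State that improvement will be described as preliminary only if the interval excludes no change on the improvement side, and that an interval including no change is inconclusive. Reconcile this with the POCL intervention term in 12.3 and 12.4, which has no comparator in Group A alone.
2. **Sections 7 and 10.1.** Leave the dated 10.20.20 entries as they are. Add a dated clarification that whether the aim was met will be judged from the 3.2 endpoint.
3. **Sections 12.2 and 12.4.** Size the larger study from a pre-specified smallest worthwhile frailty difference. Take from the pilot only the SD of change, at an upper confidence limit, and retention.

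The cost is wording, with no new participants or data. The downside is that the pilot will often return an inconclusive result: the interval excludes no change in only about 35–54% of pilots at a true change of 0.37–0.48 SD, under the same assumptions.
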